8 STUDY PROCEDURES

8.1 Visit Schedule

Table 4. Required Protocol Assessments

	Screening			Temporary SCS Trial Phase			Permanent SCS Implant Phase			
	Baseline	Trial Procedure/ Post-procedure	Trial End (≤30 days)	Implant Procedure (Day 0)/ Post-procedure	1 Month (30 days -14 days, +21 days)	3 Month (90 days ± 21 days)	6 Month (180 days ± 30 days)	12 Month (365 days ± 60 days)	18 Month (545 days ± 90 days)	24 Month (730 days ± 90 days)
Protocol Assessments	X									
Informed Consent & Inclusion/Exclusion	X									
Baseline Evaluation	X									
Procedure ¹		X	X	X						
Imaging ²		X	X	X						
Investigator Evaluation										
Study Pain Assessment	X		X		X	X	X	X	X	X
Medications	X	X	X	X	X	X	X	X	X	X
Safety ³	X	X	X	X	X	X	X	X	X	X
Subject Questionnaires										
PROMIS-29+2	X		X		X	X	X	X	X	X
PROMIS-10 Global	X		X		X	X	X	X	X	X
POMS 2-A Short	X		X		X	X	X	X	X	X
PGIC & Patient Satisfaction			X		X	X	X	X	X	X
Stimulation Characteristics			X		X	X	X	X	X	X
Neurophysiological Data										
Posture Change Measurements		X			X	X	X	X	X	X
Neurophysiological Measurements ⁴	X		O	X	X	X	X	X	X	X
Programming ⁵	X		X	O	O	O	O	O	O	O

Additional Optional Assessments ⁶	O	O	O	O	O	O	O	O	O	O	O

X = Required; O = Optional

¹ Trial procedure, trial end lead pull procedure, or permanent implant procedure.

² X-rays (AP and lateral) will be taken during the trial, implant, and revision/replacement procedures per standard of care. Additionally, X-rays (AP and lateral) are required prior to lead pull at Trial End and prior to the 1-month visit post-permanent implant. Fluoroscopy may substitute for X-ray. Additionally, imaging (e.g., X-ray, CT) may be taken at any time during the study in order to evaluate potential AEs, as needed and determined by the physician.

³ Includes evaluation for potential adverse events, device deficiencies, and protocol deviations.

⁴ Neurophysiological measurements may occur over more than one visit. Neurophysiological measurements for the trial and implant procedure need not be collected on the procedure date; they may be collected prior to and including trial end or the 1-month visit window, respectively. At follow-up, activation plots must be collected on the follow-up visit date; however, other neurophysiological measurements (e.g., conduction velocity, chronaxie, rheobase) may be collected any time within the visit window.

⁵ Initial programming will follow the trial procedure and following the permanent implant procedure (prior to the day of the 1-month follow-up visit); it need not occur on the procedure date. Reprogramming may occur as needed for optimization throughout the study.

⁶ Additional optional assessments may be requested any time during the study that subjects can elect to participate in.

8.2 Screening/Baseline Evaluation

Potential study subjects will be identified and informed of the study. Subjects who provide informed consent for study participation (refer to section 13.2.2) will complete the study-specific baseline assessments. Medical records documenting the condition of the subject, including relevant previous medical history and results of diagnostic tests, will be obtained. Data collected during screening/baseline include:

- Determination of subject study eligibility (inclusion/exclusion criteria)
- Demographics, medical history, and physical examination
- Study Pain Assessment (including DN4 and pain etiology/pathophysiology)
- PROMIS-29+2
- PROMIS-10 Global
- POMS 2-A Short

8.3 Enrollment

Subjects who provide informed consent and meet eligibility criteria will be considered enrolled at the time of the trial procedure.

8.4 Temporary SCS Trial Phase

Before permanent implant of the Evoke System, subjects will undergo a trial stimulation phase with the external stimulator attached to one or two Evoke leads. The procedure will be performed in accordance with standard of care and the Evoke IFU. The device will be programmed for pain coverage in accordance with the Evoke IFU. Timing of post-procedure programming will occur at the discretion of the Investigator.

The trial will last up to 30 days (typically 1 week) to determine if the subject will proceed to the permanent implant. Subjects may have multiple visits during the trial phase in order to optimize stimulation settings. The following data will be collected during the trial phase:

Trial Procedure/Post-procedure:

- Trial procedure data
- X-rays (AP and lateral) during the procedure
- Posture change measurements (to be collected at least once post-procedure through Trial End)
- Neurophysiological measurements (to be collected at least once post-procedure through Trial End)
- Device programming

Trial End:

- Study Pain Assessment
- PROMIS-29+2
- PROMIS-10 Global
- POMS 2-A Short
- PGIC & Patient Satisfaction
- Stimulation characteristics
- Posture change measurements (to be collected at least once post-procedure through Trial End)
- Neurophysiological measurements (to be collected at least once post-procedure through Trial End)
- X-rays (AP and lateral) prior to lead pull
- Lead pull procedure

8.5 Implant Procedure/Post-procedure

Subjects will be approved to undergo implantation of the Evoke System if the subjects' trial was successful based on physician and subject determination.

The permanent implant will involve the implantation of the Evoke stimulator and one or two Evoke leads. The implant procedure will be performed in accordance with standard of care and the IFU, and programming will be performed in accordance with the IFU. Timing of post-procedure programming will occur at the discretion of the Investigator, prior to the 1-month follow-up visit.

The following data will be collected during the implant procedure/post-procedure:

- Implant procedure data
- X-rays (AP and lateral) during the procedure
- X-rays (AP and lateral) post-procedure, prior to 1-month follow-up
- Neurophysiological measurements (optional)
- Device programming

8.6 Follow-up Visits

Subjects will be followed-up at 1 month (30, -14 days, +21 days), 3 months (90±21 days), 6 months (180±30 days), 12 months (365±60 days), 18 months (545±90 days), 24 months (730±90 days). Subjects may have their device reprogrammed throughout follow-up. The following data will be collected during follow-up:

- Study Pain Assessment
- PROMIS-29+2
- PROMIS-10 Global
- POMS 2-A Short
PGIC & Patient Satisfaction
- Stimulation characteristics
- Posture change measurements
- Neurophysiologic measurements
- Device programming (as needed)

8.7 Programming Sessions

Device programming will initially occur following the trial and implant procedures. Programming adjustments may occur as many times as needed after initial programming (for either the trial or the permanent implant) to optimize treatment. Programming will be performed in accordance with the IFU by the Sponsor representative.

8.8 Revisions, Replacements, and Explants

During the study subjects may require a device revision, replacement or explant. The following data will be collected for revisions, replacements, and explants:

- Revision/replacement/explant procedure data
- Adverse Events
- Device deficiencies
- X-rays (as needed)
- Neurophysiologic measurements (optional)

8.9 Study Exit – Completion and Withdrawal

At the end of the subjects' study participation, either due to study completion or early withdrawal, a study exit form will be completed documenting the date and reason for study exit. The study exit form

is only required for enrolled subjects. For those subjects who miss a scheduled study visit, the site shall attempt to contact the subject at least three times, with at least one attempt being a certified letter, prior to considering the subject lost to follow-up (LTF). For subjects who withdraw from the study early, all attempts will be made to collect safety data.

8.10 Concomitant Medications

Medications will be collected at baseline and changes will be tracked throughout the subjects' participation in the study.

9 ADVERSE EVENTS

9.1 Adverse Event Definitions

9.1.1 Adverse Event

An **adverse event (AE)** is defined as any untoward medical occurrence, unintended disease or injury, or untoward clinical signs in subjects, whether or not related to the investigational medical device.

9.1.2 Serious Adverse Event

A **serious adverse event (SAE)** is defined as an AE that

- Led to death,
- Led to serious deterioration in the health of the subject, and that either resulted in:
 1. a life-threatening illness or injury, or
 2. a permanent impairment of a body structure or a body function, or
 3. prolonged hospitalization, or
 4. medical or surgical intervention to prevent life-threatening illness or injury or permanent impairment to a body structure or a body function,
- Led to fetal distress, fetal death, or congenital anomaly or birth defect.

Note: Planned hospitalization for a pre-existing condition or a procedure required by the protocol (e.g., the index implant procedure, or device replacement due to normal battery depletion or lead migration), or a hospitalization without serious deterioration in health, is not considered an SAE.

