9.2 Adverse Event Recording and Reporting

9.2.1 Adverse Event Recording

Investigators are responsible for providing a description of all AEs, including the clinical outcome for the subject. Investigators will evaluate each event for seriousness, severity, and relatedness to the procedure, device, or stimulation therapy. Investigators must supply the Sponsor with any additional information related to safety reporting of a particular event.

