11.3 General Statistical Procedures

The following general statistical methods will be employed to assess the study data:

- There are no pre-planned formal statistical hypothesis tests.
- Standard summary statistics will be used to summarize key study variables. Categorical variables will be summarized via incidence and percent. Continuous variables will be summarized via mean, median, standard deviation, and range.
- Findings of significance may be presented and include p-values and/or 95% confidence intervals as appropriate.
- Standard tests for significance will be employed, including one sample t-tests. Additional exploratory analyses may be performed and include correlation analysis, linear and logistic regression analyses, repeated measures analyses, and generalized estimating equation (GEE) analyses as appropriate.
- Unless stated otherwise, statistical significance is defined as achieving a p-value less than 0.05. P-values will be nominal and not adjusted for multiplicity.
- In the event planned parametric methods are found to be inappropriate based upon observed distributions of individual variables, appropriate non-parametric methods will be employed.
- The incidence of all distinct AEs will be presented. AEs will also be summarized by seriousness, severity, and relatedness to the procedure, device, and/or stimulation. AEs will be reported based on the adjudication committee determination.

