12 RISK ANALYSIS

12.1 Potential Risks

Risks associated with the Evoke System are similar to those of other open-loop SCS systems, which are generally minor. All medical procedures involve some risk of injury, including death. Other anticipated risks associated with the Evoke System are listed in this protocol or found in the literature, post-market surveillance data (e.g., FDA Manufacturer and User Facility Device Experience (MAUDE) database), and device labeling for SCS systems. Please refer to the current Evoke IFUs for the most up-to-date risks associated with the Evoke System.

In addition to the general surgical risks, potential risks to subjects associated with implantation and use of the Evoke System include, but are not limited to:

- Undesirable changes in stimulation sensation and/or location
- Uncomfortable changes in stimulation (over and/or under stimulation)
- Persistent post-surgical pain at hardware implantation sites
- CLS migration, which may result in pain or difficulty in charging
- Seroma or hematoma at surgery sites
- Epidural hemorrhage, spinal cord injury and possible paralysis
- Lead migration from the location chosen at initial implantation resulting in stimulation changes
- Breakage of the lead or failure of other system components, which may result in loss of stimulation
- Rejection of, or allergic reaction to, the implanted components
- Infection that may require hospitalization with intravenous antibiotic therapy
- Cerebrospinal fluid (CSF) leakage
- Inadequate pain relief following system implantation
- Erosion of the lead or CLS through the skin
- Weakness, clumsiness, numbness or pain

Subjects may require surgery (including revision, explant, and replacement) as a result of any of the above.

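### Section 9.1.2 counts hospitalization as serious only when it is prolonged, so an unplanned new admission of ordinary length can fall outside the SAE definition, which fits poorly with the section's own Note

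*Combined protocol and SAP*

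**What the plan says.** Section 9.1.2 makes an event an SAE if it led to death, to one of the listed fetal or congenital outcomes, or to a two-part condition. The lead-in to that condition is "Led to serious deterioration in the health of the subject, and that either resulted in", and four items follow:

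- Item 1 is a life-threatening condition.
- Item 2 is permanent impairment.
- Item 3 is "prolonged hospitalization, or".
- Item 4 is "medical or surgical intervention to prevent life-threatening illness or injury or permanent impairment to a body structure or a body function".

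The Note beneath the list removes two kinds of stay. The first is "Planned hospitalization for a pre-existing condition or a procedure required by the protocol", with the index implant among its examples. The second is worded "or a hospitalization without serious deterioration in health, is not considered an SAE". Neither exemption mentions how long the stay lasts.

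Section 9.2.1 has the investigator rate first: "Investigators will evaluate each event for seriousness, severity, and relatedness to the procedure, device, or stimulation therapy". Section 9.3 then sends all AEs to an independent medical reviewer and/or adjudication committee, whose determination is the one reported. For the analysis, section 11.3 states: "AEs will also be summarized by seriousness, severity, and relatedness to the procedure, device, and/or stimulation".

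**The concern.** Item 3 can be read as a long stay or as the extension of a stay already under way. On neither reading does it cover a patient who deteriorates seriously, is admitted unexpectedly for a few days and recovers. The Note reads as though the authors expected admission to count, since it takes the trouble to exempt planned stays.

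The affected events are foreseeable. Section 12.1 lists "Infection that may require hospitalization with intravenous antibiotic therapy" and also cerebrospinal fluid leakage.

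SAE incidence is a main safety output of a single-arm descriptive study. Section 2.5 gives continuing evidence of device safety as a reason for the study, and section 13.11 names the incidence and seriousness of AEs among the grounds for suspension or termination. Section 11.4 allows analyses at any time, so a table could be produced under the unreconciled wording.

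**Working it through.** This is a check of wording; the plan gives no figure to reproduce. I applied the list in 9.1.2 and then the Note to each type of admission.

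1. **Admission without serious deterioration.** It fails the lead-in, and the Note also exempts it. List and Note agree: not an SAE.
2. **Planned stay for the index implant, of ordinary length.** It meets no item, and the Note exempts it. They agree: not an SAE.
3. **Existing stay extended by an event with serious deterioration.** Item 3 is met if prolonged means extended. If it means a long stay, the answer depends on a length that the section does not give.
4. **Unplanned new admission of ordinary length, with serious deterioration, meeting item 1, 2 or 4.** It is an SAE whatever item 3 says.
5. **The same admission meeting none of items 1, 2 and 4.** Item 3 is not met on either reading, so the list makes it non-serious. The Note does not exempt it, and its exemption of planned stays suggests that an unplanned one was meant to count.

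Only case 5 is the gap, with the undefined term in case 3 as a lesser part of the same problem.

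Two listed risks show how the gap arises:

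- For an infection admitted for a short course of intravenous antibiotics, seriousness turns on item 4: did the rater judge that treatment averted a life-threatening condition or permanent impairment?
- A cerebrospinal fluid leak with marked symptoms, two nights in hospital and full recovery may meet none of the four items, depending on what intervention was given and why.

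No other section adds a criterion for a new admission. Section 9.3 assigns adjudication but states no separate rule for seriousness.

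On size, the number of subjects affected would be N × a × u. Here N is the number enrolled (up to 300), a is the proportion with an unplanned ordinary-length admission with serious deterioration, and u is the share of those meeting no other SAE criterion. The documents give neither a nor u. What follows from N alone, with 300 as denominator, is the effect per subject: 1/300 = 0.33 percentage points of SAE incidence for each subject whose only SAE is missed.

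**The case against.** The strongest reply is that the Note only lists exclusions and nowhere says that unplanned admissions are SAEs. Its second exemption repeats the lead-in, so it reveals nothing about intent. The planned-stay exemption has some work to do even under the present item 3, because a planned stay can become prolonged. This stands in part: there is no express contradiction. But the Note names the index implant stay without reference to length, and that makes most sense if admission as such can confer seriousness.

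A second reply is that all AEs are adjudicated, so the tables do not simply carry the readings of up to 25 sites. That is correct about differences between sites. It does not close the gap, because the adjudicators have only the same definition to apply.

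A third is that no event is lost. Subject to the exceptions in 9.2.2, AEs are still reported, and section 11.3 also summarises them by severity and relatedness. No hypothesis test depends on the SAE count. This stands and limits the consequence to the seriousness rows and to decisions that use them.

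Three stronger readings are tempting, and the documents do not support them:

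- A reader might infer that every ordinary-length unplanned admission is scored non-serious. Items 1, 2 and 4 can still apply.
- A reader might infer that unanticipated adverse device effects would be missed. Section 9.1.3 has its own wording, does not refer to the list in 9.1.2, and leaves the determination to the committee. Infection with admission and cerebrospinal fluid leakage are also already listed risks.
- A reader might attach a count. Assuming a = 1–5% and u = 25–75% gives 300 × 0.01 × 0.25 = 0.75 to 300 × 0.05 × 0.75 = 11.25 subjects, but both ranges are assumptions without support in the documents. They show scale only.

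**Conclusion.** The point holds in a limited form. As written, 9.1.2 leaves out unplanned new admissions of ordinary length with serious deterioration that meet none of items 1, 2 and 4, and it leaves prolonged undefined. This is an ambiguity with an implied inconsistency. The SAE summary can be understated, by an amount that the documents do not allow anyone to compute.

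The conclusion rests on two assumptions: that the Note's treatment of planned stays reflects an intention that admission can count, and that adjudicators apply the protocol's definition because no other is supplied. If the sponsor did intend to exclude ordinary-length admissions, the text should say so and the Note should be aligned with it. The correction is worth making because it changes which events enter a main safety table and costs little.

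**What to change.** Reconcile item 3 with the Note by rewording the item to: *unplanned in-patient hospitalization, or prolongation of an existing hospitalization*. Keep the lead-in requiring serious deterioration and keep the exemption for planned admissions. Bring any CRF completion guidance into line. Before any table by seriousness is produced, have the reviewer or committee in 9.3 re-check, under the new wording, all AEs already recorded with an admission.

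The cost is one line in an amendment, a matching guidance change and a small record review, with no added burden on subjects. The downside is that the reported SAE incidence may rise slightly.

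### The SAE Note in 9.1.2 presents device replacement for lead migration as protocol-required, which no section makes it, and so can remove the serious label from a planned hospitalization for it

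*Combined protocol and SAP*

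**What the plan says.** Section 9.1.2 defines an SAE as an AE that led to death, to a fetal outcome, or to serious deterioration in health with one of four listed results, among them prolonged hospitalization. A Note then removes certain hospitalizations. One alternative covers planned hospitalization for "a procedure required by the protocol (e.g., the index implant procedure, or device replacement due to normal battery depletion or lead migration". The sentence ends with a further alternative: "or a hospitalization without serious deterioration in health, is not considered an SAE".

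Other sections describe the same surgery differently:

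- **8.1, Table 4, footnote 1** defines the Procedure row as "Trial procedure, trial end lead pull procedure, or permanent implant procedure". Footnote 2 says that X-rays are taken at revision or replacement procedures as part of standard care.
- **8.8** states: "During the study subjects may require a device revision, replacement or explant". It then lists the data to collect if one takes place.
- **12.1** includes among the risks of implantation and use "Lead migration from the location chosen at initial implantation resulting in stimulation changes", and closes the list with "Subjects may require surgery (including revision, explant, and replacement) as a result of any of the above".

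The serious label is used in 11.3: "AEs will also be summarized by seriousness, severity, and relatedness to the procedure, device, and/or stimulation". Section 13.11 also gives the incidence and seriousness of AEs as one possible reason for stopping the study.

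**The concern.** A protocol-required procedure is normally excluded from the SAE definition because every subject is scheduled to have it, so the admission says nothing about harm. The index implant fits that reasoning. A reoperation because a lead has moved does not, since it follows from a risk that the protocol itself attributes to the device. Calling it protocol-required settles the seriousness question by its label and not by what happened to the subject.

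Section 2.5 says that the study is meant to add evidence on device safety. For one listed device risk, the Note can only move an event from serious to non-serious. Someone reading the seriousness table alone, without the definition behind it, would not see that this had been done.

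**Working it through.** The plan gives no figure on this point and no arithmetic applies. The check is a comparison of the texts.

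**Step 1. Is replacement for migration required anywhere?** Footnote 1 to Table 4 names three procedures, and replacement is not among them. Footnote 2 governs imaging if a replacement takes place and does not call for one. Section 8.8 makes replacement depend on the subject's need. Section 12.1 describes it as surgery that may follow from a listed risk. No section requires it, so the Note's example does not match the category it is meant to illustrate. The same is true of replacement for normal battery depletion, but that is expected in the life of a device and is not on the 12.1 risk list.

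**Step 2. Does the last clause of the Note limit the exclusion?** That clause repeats its noun and is joined by *or*, so it is a separate ground for exclusion and not a condition on the one before it. The planned-procedure exclusion therefore applies whether or not health seriously deteriorated.

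**Step 3. When do the words *or lead migration* change a classification?** Take a hospitalization for migration replacement:

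| Situation | Note as written | With the words deleted |
|---|---|---|
| Planned, no serious deterioration | Not an SAE | Not an SAE (last clause still excludes it) |
| Planned, serious deterioration, no listed result | Not an SAE | Not an SAE (definition not met) |
| Planned, serious deterioration, prolonged hospitalization | Not an SAE | SAE |
| Unplanned | Note's planned-procedure ground does not apply | Same |
| Death, life-threatening event, permanent impairment or fetal outcome | Note concerns hospitalization only; these criteria stand | Same |

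Only the third row changes. In the first two the words are redundant. In the third they remove the label where the ordinary definition would give it. The table takes prolonged hospitalization as the result clearly reached, because the Note speaks of hospitalization. Whether it would also be read to override the criterion on medical or surgical intervention is not settled by the text, and the point does not need it.

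**Step 4. Would a later step correct it?** Investigators rate seriousness under 9.2.1, and an independent reviewer or committee adjudicates all AEs under 9.3. The document gives neither any definition of an SAE other than 9.1.2, and no text allows the Note to be set aside.

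**Step 5. What survives?** Section 8.8 collects procedure data, AEs and device deficiencies at each replacement. A migration reported as an AE remains in the 11.3 summaries of incidence, severity and relatedness. Only the serious label is at issue.

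**The case against.** The strongest reply is that the third row may be empty. A planned admission is not in itself a prolonged one, and if a complication lengthens the stay, that complication can be judged as an AE of its own. Section 12.1 describes migration mainly as a change in stimulation, and 9.2.2 keeps typical stimulation changes, and loss of therapy without an untoward medical occurrence, out of AE reporting. Most elective replacements would therefore never reach serious deterioration, and the last clause would exclude them anyway. This stands, and it limits the point to a minor one. It does not justify the wording, because words that are either redundant or wrong can be removed without loss.

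It can also be said that the battery-depletion example is no more required than the migration example, so deleting one leaves a loose category. That is correct. The difference is that battery depletion in normal use is an expected event, while migration is a listed risk, so only the second can hide a device-related harm.

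Three stronger readings are tempting, and the documents support none of them:

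- A reader might infer that the study's SAE rate will be materially understated. The documents give no migration, replacement or hospitalization rate from which to judge this.
- A reader might take the cap of 300 enrolled subjects as the denominator and work out a minimum shift per reclassified subject. Section 11.3 states no safety denominator, and AEs are reportable from consent, which comes before enrollment at the trial procedure.
- A reader might infer that reoperations for lead breakage, another 12.1 risk, will be classified differently because the Note does not name it. The examples open with *e.g.*, so the omission shows nothing either way.

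**Conclusion.** The Note misdescribes replacement for lead migration as protocol-required. Read literally, it withholds the serious label from a planned hospitalization for that surgery even when the SAE definition would otherwise be met. Any error runs in one direction only, towards fewer SAEs.

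The importance is minor. Few events, and perhaps none, would be affected, and no size can be calculated from the documents. The safety record itself is kept. The study has no pre-planned formal hypothesis tests, and no conclusion is shown to change.

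The verdict rests on two readings: that the clauses of the Note are alternatives, and that sites and adjudicators apply the Note as written. If they in practice required absence of serious deterioration throughout, the words would have no effect, and deleting them would still be harmless.

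**What to change.** In the 9.1.2 Note, delete *or lead migration*. Each hospitalization for migration replacement is then judged against the ordinary SAE definition, and those without serious deterioration remain excluded by the last clause. Replacement for normal battery depletion may stay as an expected event in the device's life, although no section requires it either.

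The cost is a three-word amendment with sponsor and IRB approval under 13.10, and a re-check of any such hospitalizations already classified. The SAE count may rise slightly. No new data are needed.
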